### PMTCT Knowledge

19. Mine man kod tuo mar ayaki, ma kute gi okyanl fweny onego opim nyadidi ndalo ma gi dhodho nyathi?
- Bang dweche adek
  - Bang dweche auchiel
  - Bang dweche apar kod ariyo
  - Mana, seche ma nyathi oweyo dhoth
20. Mine man kod kute mag ayaki onego we mwonyo yath mar ART karang'o?
- Nyaka nyathi chak chamo chiemo mapek, ka osechopo dweche auchiel.
  - Nyaka nyathi we dhoth.
  - Nyaka yudni nyathi onge kute mag ayaki bang pim ka osechopo dweche 18
  - Ooyo, min nyathi onego dhi mbele kod mwonyo yath mondo orit ng'imane.
21. Dwarore ni nyithindo mondo opim kute mag ayaki seche madwarore nayaka girom nade?:
- Dweche auchiel
  - Dweche apar kod ariyo
  - Dweche apar kod aboro
  - Higni ariyo
  - Ka nyathi oweyo dhoth

#### PMTCT Motivation

Kuom weche gi, ere ma iyiego kata idagi.

SD=strongly disagree, D=disagree, N=neither agree nor disagree, A= agree, SA = strongly agree.

|   | Adagi Ahinya | Adagi | Man e diere | Ayie | Ayie Ahinya |
|---|--------------|-------|-------------|------|-------------|
| 22. Angeyo ni anyalo luwora kod thieth kaka dwarore seche ma nyathina pod tin kendo dhoth           |              |       |             |      |             |
| 23. Miyo nyathi yathe en gima maber kuoma   |              |       |             |      |             |
| 24. Kata ka nyathi ok dwa yath, to angeyo ni abiro miye yath kaka dwarore                           |              |       |             |      |             |
| 25. Ber mondo nyatho oyud pim mar viral seche duto ndalo mapod odhoth                               |              |       |             |      |             |
| 26. Dich moko machalo kaka tich, tije ot, rito nyathi nyalo mona mondo oyud pim mar dweche auchiel. |              |       |             |      |             |
| 27. Tero nyathi e thieth seche madwarore en gima ger ahinya   |              |       |             |      |             |

|  | Adagi ahinya | Adagi | Man e dierel | Ayie | Ayie Ahinya |
|--|--------------|-------|--------------|------|-------------|
| 28. Chunya chandre ni ka atero nyathina e pim e od thieth to wanyalo yudo tuo mar covid -19  |              |       |              |      |             |
| 29. Weche mag wuoth dhi kendo duogo ka aa e od thieth(weche pesa kata yudo gari/apiko) kalure kod tuo mar covid 19 ne omiyo adeko, kata koso yudo thieth |              |       |              |      |             |
| 30. Ne adeko yudo thieth kata dhi e od thieth mondo,nikech ne atuo kendo ne ok adwa ni mondo ami ji tuo  |              |       |              |      |             |

#### Assessing delivery VL as intervention

Kiyie to nyiswa Tarik kod higa mane remo mar VL ne okau, dwoko mag pim, to kod gima omiyo ne otim pim are nyaka ne ibed mayach. Kiyie to we nono kar dwoko penjo ka remo ne ok okau.

31. Pim mokwongo nyaka ne yud ni in kod ich
- Tarik mar pim mokwongo** \_\_\_\_\_
  - Dwoko mokwongo( yier achiel)
    - Ofwenyore
    - Ok ofwenyore
    - Ne ayudo dwoko, to ok apar ni ne en nade
    - Ne ok onyisa dwoko
  - Gima omiyo ne otim pim
    - Pim ma pile mar VL
    - Iluwo godo pim mar VL mane ofwenyore
    - Nonro

- iv. Ok ang'eyo
- 32. Pim mar ariyo nyaka ne yud ni in kod ich
  - d. **Tarik mar pim mar ariyo** \_\_\_\_\_
  - e. Dwoko mar ariyo(yier achiel)
    - i. Ofwenyore
    - ii. Ok ofwenyore
    - iii. Ne ayudo dwoko, to ok apar ni ne en nade
    - iv. Ne ok onyisa dwoko
  - f. Gima omiyo ne otim pim
    - i. Pim ma pile mar VL
    - ii. Iluwo godo pim mar VL mane ofwenyore
    - iii. Nonro
    - iv. Ok ang'eyo
- 33. Pim mar adek nyaka ne yud ni in kod ich
  - a. **Tarik mar pim mar adek** \_\_\_\_\_
  - b. Dwoko mar adek (yier achiel)
    - i. Ofwenyore
    - ii. Ok ofwenyore
    - iii. Ne ayudo dwoko, to ok apar ni ne en nade
    - iv. Ne ok onyisa dwoko
  - c. Gima omiyo ne otim pim
    - i. Pim ma pile mar VL
    - ii. Iluwo godo pim mar VL mane ofwenyore
    - iii. Nonro
    - iv. Ok ang'eyo
- 34. Pim mar angwen nyaka ne yud ni in kod ich
  - a. **Tarik mar pim mar angwen** \_\_\_\_\_
  - b. Dwoko mar angwen (yier achiel)
    - i. Ofwenyore
    - ii. Ok ofwenyore
    - iii. Ne ayudo dwoko, to ok apar ni ne en nade
    - iv. Ne ok onyisa dwoko
  - c. Gima omiyo ne otim pim
    - i. Pim ma pile mar VL
    - ii. Iluwo godo pim mar VL mane ofwenyore
    - iii. Nonro
    - iv. Ok ang'eyo

#### Engagement with HITSystem 2.1 - **INTERVENTION ONLY**

- 35. Nyaka ne ichak dhi e ANC, bende iseyudo sms moro a mora ka oa hospital?
  - a. Ooyo,Pok ayudo sms.
  - b. Eeh, Aseyudo achiel, to ma ok ngeny ne adek
  - c. Eeh, aseyudo kind sms 3 kod 5,
  - d. Eeh, Aseyudo sms mohewo
- 36. Bende iseyudo sms moro a moro mapenji wechegi?
  - a. Ngeyo kaka idhi.....Yes / No
  - b. Manyisi chieng ma onego iduogie e hospital..... Yes / No
  - c. Maparoni mondo imwony yath..... Yes / No
  - d. Maparoni mondo iter nyathi e hospital.....Yes / No
  - e. Manyisi mondo idog e hospital mondo inge chal dwako nyathi..... Yes / No
- 37. Kane I yie ne iyudo sms e no 33, kiyie to dwokie penjo no 34 kaka ne itimo bang yudo sms, ka ok kamano to dhie no 35:
  - a. Sms go ne ok okonya.....True / False
  - b. Sms ne okonya mondo apar amwony yath.....True / False
  - c. Ne an kod chandruok ni ngato nyalo neon sms ma ng'e godo chal mara.....True / False
  - d. Sms ne omiya abedo kod e achiel gi hospital/jo thieth.....True / False
  - e. Sms ne omiyo anyalo pare chieng ma onego adogie e hospital.....True / False
  - f. Ng'ato ma opgre koda ne osomo sms ma openja.....True / False
  - g. Ja family kata osiepnna ne ongeyao chal mara nikech sms no.....True / False

- h. Sms ne omiya weche mabeyo kaluwore kod thieth mar nyathina.....True / False
  - i. Sms ne omiya mijingo mondo amend dhi mbele kod yudo thieth mar  
PMTCT/EID.....True / False
38. Kiyie to yier seche ma diher ni mondo waparni godo seche ma onego imwony ART
- a. Okadwar,, kik uorna sms
  - b. Pile
  - c. Juma
  - d. Bang juma 2
  - e. Dwe ka dwe

## Appendix IIF. Data Collection Tool For Home-based Sample Collection

### For all home-visits:

1. ID Ja chiwre e nonro \_\_\_\_\_
2. Tarik mar nonro \_\_\_\_\_
3. Nying Ja nonro \_\_\_\_\_
4. Utimo limbe nang'o?
  - a. Pim VL mar nyuol
  - b. Pim VL mar dweche auchiel
  - c. Mamoko,ler ane \_\_\_\_\_
5. Jotijwa osetimo limbe e dalani kae nyadidi?
  - a. Achiel
  - b. Ariyo
  - c. Adek
  - d. Ang'wen kata mangeny
6. Ja chiwre e nonro be oyudre?
  - a. Dala
  - b. Oonge dala
  - c. Odar odhi kama chielo
  - d. Ne osetho
7. Be nitie ng'ato e dala (ma opogore kod nyathi ngat ma obi lim)?
  - a. Eeh, Jahera ja chiwre e nonro
  - b. Eeh, Nyithind ja chiwre e nonro
  - c. Eeh, Anyuola ja chiwre e nonro (ng'a giri \_\_\_\_\_)
  - d. Eeh, osiep kata jirani ja chiwre e nonro
  - e. Ooyo, ja chiwre e nonro nitie kende
8. Ka iyie ni eeh e (a, b, c, or d) e penjo mar 7: Be isenyiso jogi duto mantie e dalani chal mari mar ayaki?
  - a. Eeh
  - b. Ooyo
  - c. Ok ong'ere

**Ka ng'ato nitie e dala ma opogore kod ja chiwre e nonro kod nyathine, to ne pok onyiso ng'ato a ng'ata chal mare mar ayaki, weche ma iye kendo mopondo nyalo ngere. Yier chieng machielo mar timo pim mar VL kod EID, to ka ber ne ni weche ma opondo mag ja chiw nonro ok ongere kata matin. Dhi nyime kod penjo (penjo 9-14).**

**Ka ngato onge e dala to ja chiw nonro nitie kod nyathine, kata ka jachiw nonro asenyiso ji e dala chal mare mar ayaki,kare koro dhi nyime kod penjo 15-20**

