**Participant tracking for VL among participants 'lost to follow-up' (LTFU).** Measurement of viral suppression rates in either study arm can be skewed if detectable VL is more/less frequent in LTFU patients. Therefore, we will use a weighted sampling-based approach to track patients who receive no delivery VL test or postpartum VL test within 6 months. From a twice monthly LTFU patient list for each site, participants will be targeted for active tracking including phone calls and home visit to reach women who disengaged from care prior to or by the time of delivery, and thus had no VL sample collected at the time of delivery. Study staff conducting home visits (mentor mother and community health worker) will be thoroughly trained on protection of confidentiality, especially when participants are not home or have relocated. Visits will be introduced as well-baby visits to protect confidentiality, and a dried blood spot sample (DBS) for VL will only be collected once privacy is confirmed and consent provided. Visits will be rescheduled if privacy is perceived to be compromised at any time. Women whose infant has not yet tested for HIV will be offered sample collection for infant testing, and DBS will be transported for processing (Appendix 2F, Home Visit Survey).

**Objective 2 Outcomes.** The primary outcome for Objective 2 is the proportion of clients with a detectable VL at delivery and within 6 months postpartum. Given the ongoing shortage of VL testing in the country, all women who have not received a postpartum VL test by 6m postpartum will be offered a "study-initiated" VL test. These samples will be collected and shipped in the same manner as the delivery VL test and will be supported by study funds and sent to the KEMRI CDC lab for processing. Furthermore, at the 6m visit, infants will be offered an HIV PCR test, which will also be sent to KEMRI CDC lab. Participants who receive these "study-initiated" tests will not be considered "completely retained" for the aim 1 primary outcome; however, these data are necessary for the aim 2 outcome. Secondary outcomes associated with Objective 2 will include VL test coverage (proportion with VL test in antenatal and postpartum periods, per guidelines), VL

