## Appendix IIF. Data Collection Tool For Home-based Sample Collection

### For all home-visits:

1. Participant ID \_\_\_\_\_
2. Date of visit \_\_\_\_\_
3. Person conducting visit \_\_\_\_\_
4. Reason for visit
  - a. Birth VL test
  - b. 6-month VL test
  - c. Other, please specify \_\_\_\_\_
5. How many times have study staff attempted to reach this participant through a home visit?
  - a. 1
  - b. 2
  - c. 3
  - d. 4 or more
6. Participant's status
  - a. Home
  - b. Not at home
  - c. Moved to different location
  - d. Deceased
7. Is anybody (other than the participant's infant) home?
  - a. Yes, participant's partner
  - b. Yes, participant's non-infant child or children
  - c. Yes, participant's other family member (please specify who \_\_\_\_\_)
  - d. Yes, participant's neighbor or friend
  - e. No, participant is alone
8. If YES (a, b, c, or d) to question 7: Has the participant disclosed her HIV status to all people who are currently at her home?
  - a. Yes
  - b. No
  - c. Unknown

**If anyone is home, other than the participant and her infant and she has not disclosed or her disclosure status is unknown, privacy and confidentiality may be compromised. Reschedule VL and EID test (if applicable) to ensure patient confidentiality. Proceed with "well-baby" visit (Questions 9-14).**

**If no-one is home, other than participant and her infant, OR she has disclosed her HIV status to everyone in the home, please proceed to questions 15 - 20**

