## Kiambatisho F. Kijalada chana ukusanyaji taarifa kwa sampuli zitazo tolewa Nyumbani

### Kwa matembezi yote ya nyumbani:

1. Nambari ya mshiriki \_\_\_\_\_
2. Tarehe ya kutembelewa \_\_\_\_\_
3. Anaye mtembelea \_\_\_\_\_
4. Sababu ya kumtembelea:
  - a. Kipimo cha kiwango cha virusi – Wakati wa kujifungua
  - b. Kipimo cha kiwango cha virusi - Miezi 6
  - c. Sababu nyingine, tafadhali eleza \_\_\_\_\_
5. Je, ni mara ngapi, wafanyikazi wa utafiti, wamejaribu kumfikia mshiriki kupitia ziara ya nyumbani?
  - a. 1
  - b. 2
  - c. 3
  - d. 4 au Zaidi
6. Hali ya mshiriki:
  - a. Yupo nyumbani
  - b. Hayupo nyumbani
  - c. Amehama eneo tofauti
  - d. Amefariki/Marehemu
7. Kuna mtu yeyote (mbali na mtoto wa mshiriki) nyumbani?
  - a. Ndio, mpenzi wa mshiriki
  - b. Ndio, mtoto/Watoto wa mshiriki wasio wachanga
  - c. Ndio, mtu mwingine katika familia ya mshiriki (tafadhali taja nani \_\_\_\_\_)
  - d. Ndio, jirani au rafiki ya mshiriki
  - e. Hapana, mshiriki yuko peke yake
8. Kama ni ndio kwa (a, b, c, ama d) katika swali nambari 7: Je, mshiriki amefichua hali yake ya VVU kwa watu wote walio nyumbani kwake kwa sasa?
  - a. Ndio
  - b. Hapana
  - c. Haijulikani

**Ikiwa yuko mtu mwingine nyumbani, mbali na mshiriki na mtoto wake, na mshiriki hajafichua hali yake au hali yake haijulikani, usiri unaweza kuathirika. Tafadhali badili ratiba ya upimaji kiwango cha virusi (VL), au Upimaji wa mtoto (EID) ili kuhakikisha usiri kwa mshiriki umehifadhiwa. Endelea na maswali ya kwaaidi ya ziara ya kujilia mtoto hali (Maswali 9 – 14).**

**Ikiwa hakuna mtu mwingine nyumbani, mbali na mshiriki na mtoto wake, AU, Iwapo mshiriki amefichua hali yake ya VVU kwa kila mtu anayeishi nyumbani, tafadhali endelea na maswali 15 – 20.**

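### The Luo home-visit form does not carry over the English stop/go privacy rule: it omits the unknown-disclosure trigger and the requirement that all those present know

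*Combined protocol and SAP*

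**What the plan says.** Appendix IIF exists in English, Swahili and Luo. Item 7 records who else is at home. Item 8 asks whether the woman has disclosed her HIV status to all of them, with answers Yes (8a), No (8b) and Unknown (8c). An instruction below item 8 turns these answers into an action: either a well-baby visit with sampling rescheduled (items 9-14), or items 15-20, which cover the viral load sample, the survey, where she obtains HIV services and the infant HIV test.

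- **English.** Reschedule if another person is home and "she has not disclosed or her disclosure status is unknown, privacy and confidentiality may be compromised". Proceed if nobody else is there, or if "she has disclosed her HIV status to everyone in the home".
- **Swahili.** The reschedule rule keeps both triggers: "na mshiriki hajafichua hali yake au hali yake haijulikani". The proceed rule keeps every person: "amefichua hali yake ya VVU kwa kila mtu anayeishi nyumbani".
- **Luo.** Reschedule if another person is home "to ne pok onyiso ng'ato a ng'ata chal mare mar ayaki" (and she has not yet told anyone her HIV status). Proceed if nobody else is home, "kata ka jachiw nonro asenyiso ji e dala chal mare mar ayaki,kare koro dhi nyime kod penjo 15-20" (or if she has told people at home, go on to items 15-20).

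In the protocol body, the Objective 2 methods say that a dried blood spot "will only be collected once privacy is confirmed and consent provided", and that a visit is rescheduled if privacy seems compromised. Section 8.0 (Loss of confidentiality) repeats the instruction to reschedule and relies on a home-visit checklist to reinforce it.

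**The concern.** This instruction is the only place on the form where the answer to item 8 becomes a decision. The Luo version loses two limits that the other two languages keep: the unknown trigger in the stop rule, and the word for all in the go rule. It also does not match the question printed directly above it.

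What is at stake is confidentiality. Section 8.0 names home visits as an added route to accidental disclosure of HIV status, and treats intimate partner violence as a study risk to be reported as an adverse event. The women visited are those already out of contact with care. The sample-size section says ten sites were still enrolling, so home visits lay ahead when that text was written.

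**Working it through.** No arithmetic applies. The check is a comparison of the rules, in three steps.

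**1. Are the Luo words read correctly?** The same document supplies parallels:
- *duto* stands for all in the Luo delivery survey, item 25a (all prescribed ART), and Luo item 8 on the home-visit form uses *jogi duto* for all these people.
- *ji* stands for other people in the Luo enrollment survey, item 35, with no sense of all.
- *Ok ong'ere* stands for Unknown in the Luo enrollment survey, item 16, and is option 8c on the home-visit form.
- *Pok* carries the sense of not yet in the enrollment survey, item 12 (unmarried).

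The Luo form therefore has the words for all and unknown, but its rule uses neither.

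**2. What does each rule do when another person is at home?**

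| Disclosure situation | Item 8 | English | Luo, read literally |
|---|---|---|---|
| 1. Told nobody | No | Reschedule | Reschedule |
| 2. Told some at home; another person present does not know | No | Reschedule | Stop rule not met, go rule met: proceed |
| 3. Told someone elsewhere, nobody at home | No | Reschedule | Neither rule met: no instruction |
| 4. Unknown | Unknown | Reschedule | Neither rule met: no instruction |
| 5. Told everyone present | Yes | Proceed | Proceed |

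The two forms differ in situations 2, 3 and 4. Only situation 2 gives an explicit go-ahead.

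**3. How far does this depend on the translation?**
- If *ji e dala* is taken as all the people at home, the go-ahead in situation 2 disappears. The stop rule still does not apply there, because she has told someone, so situation 2 becomes a gap.
- If the stop rule is taken as told no one here, situation 3 becomes a reschedule. Situation 2 is unchanged.
- If the stop rule is read entirely through item 8, so that No always reschedules, situations 2 and 3 are covered.
- Under each of these readings, situation 4 still has no instruction, because the unknown trigger is absent from the Luo rule.

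The explicit go-ahead thus depends on how two phrases are read. The missing unknown trigger does not.

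**The case against.** The strongest reply has four parts.

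*The English stop rule also leans on item 8.* It says she has not disclosed without saying to whom. If item 8 may complete the English, it may complete the Luo, whose item 8 keeps both limits. This has force, but the English is elliptical and can be completed, whereas the Luo names its own object (anyone at all). Reading it through item 8 means overriding what is printed. It also does not supply the missing unknown trigger.

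*The reading of Luo is unverified.* This stands. After an item about all those present, *ji e dala* could be understood as the people at home. The documents do not gloss that phrase, and the translation certificates were not available here.

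*Other controls exist.* This also stands in part. The Objective 2 methods and section 8.0 require privacy and rescheduling. The form is completed by trained staff, and the Luo form keeps English headings that restrict the sampling items to visits where confidentiality is secure. These lower the risk. They state the aim, however, while the printed rule tells staff when the aim is met. That the checklist in section 8.0 is this form is an assumption.

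*It is easy to read too much into this.* A reader might infer three further things that the documents do not support:
- That an Unknown answer permits sampling. The Luo form is silent in that case; it does not say proceed.
- That the Swahili form fails too, because its go rule speaks of those living in the home and so could miss a visiting neighbour. Its stop rule covers any other person at home and keeps the unknown trigger, and its item 8 asks about those there now.
- That a count of exposed women can be derived from the eight Siaya facilities among the twelve in Table 2. The documents do not say where each language is used. Tracing includes phone calls and a weighted sampling approach, and nothing gives the share of visits with another person present and partial or unknown disclosure.

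**Conclusion.** The Luo rule conflicts with the English rule and with its own item 8. Read literally, partial disclosure can lead to sampling with an unaware person present, and Unknown receives no instruction. The conclusion is that this can happen, not that it will.

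It rests on the Luo reading set out above, which a qualified translator must confirm; the absence of the unknown trigger is the firmest part. The size is three of five disclosure situations handled differently from the English, one of them an explicit go-ahead. No number of women can be given.

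This is a confidentiality and translation defect in an operative study form. It does not touch sample size, power or alpha. Each matched pair in Table 2 lies within one region, so if language follows region, both arms would meet the same wording. Because item 8 is intact and the protocol's general privacy rules still apply, it is a correction worth making promptly rather than one on which the trial's validity depends.

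**What to change.** Have a qualified Luo translator review the instruction after item 8, then reconcile it with the English form and with Luo item 8 by keying it to the codes:
- nobody else present (7e), or 8a: go to items 15-20;
- 8b or 8c: complete the well-baby items 9-14 and reschedule sampling.

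This adds no new rule; it restores the English one. Printing the same codes in all three languages would stop the versions drifting apart. As optional tidying, the Swahili phrase about those living in the home could be aligned with those present now.

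The cost is one corrected Luo page, a minor amendment, a short staff briefing and some more rescheduled visits. If Luo forms have already been used, a tabulation of item 8 against item 15 would show whether any sample was taken when item 8 was No or Unknown.

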**Well Baby Visit (if other person is present/confidentiality is compromised):**

9. MUAC mar nyathi \_\_\_\_\_ cm  
10. Liet mar nyathi \_\_\_\_\_ ° Celcius  
11. Nyathi dhoth nade?  
d. Maber  
e. Maber matin  
f. Marach  
12. Be nitie wach moro amora kod dhoth mar naythi? \_\_\_\_\_  
\_\_\_\_\_  
13. Be nitie wach amora kod ngima nyathi? \_\_\_\_\_  
\_\_\_\_\_  
14. Be nitie wach moro amora kod ngimani? \_\_\_\_\_  
\_\_\_\_\_  
\_\_\_\_\_

**Home visit for VL collection (if confidentiality is secure)**

15. Be remo mar VL ne okaw..... Eeh/ Ooyo  
14a. Ka en Ooyo, Ang'o ma omiyo?  
c. Ja chiwre e nonro ne otamore  
d. Mamoko, Ler ane \_\_\_\_\_  
16. Be nonro ne otieki..... Eeh/Ooyo  
a. Ka en Ooyo, Ang'o ma omiyo?  
i. Ja chiwre e nonro ne otamore  
ii. Mamoko, Ler ane \_\_\_\_\_  
17. Ja chiwre e nonro kod nyathine sani yudo thieth mar ayaki Kanye?  
f. E od thieth ma itimo e nonro  
g. E od thieth machilo, kiyie ti ler ane ni en mane \_\_\_\_\_  
h. Kod ajuoga  
i. Noweyo thieth  
j. Mamoko, mage \_\_\_\_\_  
18. Bende nyathi ne opim e od thieth kaka dwarore seche mane hike oromo(6 wks or 6 months)?..... Eeh / Ooyo  
19. **Ka en Eeh #18**, od thieth mane \_\_\_\_\_  
20. **Ka en ooyo #18**, to EID sample ne okaw kane otim limbe e dala? ..... Eeh / Ooyo  
i. Ka en ooyo #20, ang'o ma omiyo?  
a. Ja chiw nonro ne odagi  
b. Nyathi ne onge dala  
c. Mamoko,ler ane \_\_\_\_\_

